#### **1.6 Risk analysis**

This study is considered to be a non-significant risk study based on United State Food and Drug administration (FDA) and International Standards Organization (ISO) guidelines due to the daily wear nature of the study. With the potential benefit of this study, the work is considered to be ethically justifiable. Ethical approval will be sought from the University of Manchester Senate Committee on the Ethics of Research on Human Beings (hereafter referred to as Manchester UREC). The work where practical will be conducted in accordance with the ICH Good Clinical Practice Guidelines and the international standard BS EN ISO 14155:2011 'Clinical investigation of medical devices for human subjects'.

## Section 2. Resources

### 2.1 Subject selection

In this work 28 subjects will be enrolled, with an aim to complete 22 subjects.

#### 2.1.1 Subject withdrawal and replacement

This study includes four clinical visits. Once the study consent form is signed, the subject is considered to be enrolled on the study. Subjects who have signed the consent form, but who have not completed the dispensing visit will usually be replaced. All subject data will be included in the final analyses unless there are strong grounds for exclusion; such grounds will be detailed in the final report. At the end of the study, all subjects will sign a study exit form.

#### 2.1.2 Subject recruitment

Subjects will be recruited by one or more of following means:

1. Contacting volunteers on the Eurolens Research database of volunteers using email, phone and SMS.
2. Posting study details on The University of Manchester's 'Research Volunteers' website.
3. Advertising through a variety of media via a format separately approved by Manchester UREC.

#### 2.1.3 Inclusion criteria

Subjects will only be eligible for the study if:

1. They are of legal age (18) and capacity to volunteer.
2. They understand their rights as a research subject and are willing and able to sign a Statement of Informed Consent.
3. They are willing and able to follow the protocol.
4. They agree not to participate in other clinical research for the duration of this study.
5. They can be satisfactorily fitted with the study lens for a period of approximately 2 hours.
6. They can attain at least 0.20 logMAR distance high contrast visual acuity in each eye with their habitual spectacles.
7. They currently wear daily disposable soft contact lenses or have done so in the previous six months.
8. They are willing to comply with the wear schedule (approximately 2 hours on two different days)
9. They own a wearable pair of spectacles and agree to bring these to study visits.

#### 2.1.4 Exclusion criteria

Subjects will not be eligible to take part in the study if:

1. They have an ocular disorder which would normally contra-indicate contact lens wear.
2. They have a systemic disorder which would normally contra-indicate contact lens wear.
3. They currently wear reusable soft contact lenses in both eyes.
4. They are using any topical medication such as eye drops or ointment.
5. They have had cataract surgery.
6. They have had corneal refractive surgery.
7. They have any corneal distortion resulting from previous hard or rigid lens wear or have keratoconus.
8. They are pregnant or breast-feeding.
9. They have any ocular abnormality which would, in the opinion of the investigator, normally contraindicate contact lens wear.
10. They have Type 2 or greater corneal staining prior to lens application at Visit 1 or 2 [REDACTED]
11. They have corneal staining covering greater than 20% in any corneal region at Visit 1a or 2a [REDACTED]
12. They have any infectious disease which would, in the opinion of the investigator, contraindicate contact lens wear or pose a risk to study personnel; or they have any immunosuppressive disease (e.g. HIV), or a history of anaphylaxis or severe allergic reaction.
13. They have taken part in any other contact lens or care solution clinical trial or research, within two weeks prior to starting this study.

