#### 2.2 Subject discontinuation

In general, subjects should be discontinued at any time, if it is in their best interests, as judged by the investigator. Reasons for this may include clinical signs of grade 3 or more, lack of motivation, discomfort, repeated refusal to follow instructions or the use of non-study products such as solutions or lenses. Subjects will be discontinued if a serious adverse event occurs or if they miss two or more planned consecutive visits. Subjects who fail to meet all the inclusion and exclusion criteria at this time will usually be discontinued and replaced. If in the opinion of the investigator, the subject may be eligible at a later date, the subject may be brought back for up to one repeat visit of this type. Subjects may choose to leave the study at their own request. All discontinuations will be carefully recorded.

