## Section 3. Subject management

### 3.1 Visit scheduling

Subjects will be required to attend four visits across two different days.

Visit	Target	Allowable range
Visit 1	N/A	N/A
Visit 1b	2 hours after lens application	2-3 hours
Visit 2	2 days from Visit 1	2-14 days
Visit 2b	2 hours after lens application	2-3 hours

Error! Reference source not found.

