The presence of any ocular adverse events will be recorded, and reported as appropriate [REDACTED]

5. The investigator will confirm that the subject satisfies all the inclusion and exclusion criteria. Subjects who fail to meet all the criteria at this time will usually

be discontinued and replaced. If in the opinion of the investigator, the subject may be eligible at a later date, the subject may be brought back for up to one repeat visit of this type, which may include some or all of the scheduled assessments. Informed consent will not be repeated.

- 6. Study lenses will be fitted according to the randomization table and allowed to settle for five minutes. Both investigator and subject are masked from the lenses and care system used, so the lenses will be provided in lens cases which do not detail lens or care system information. If a lens fails to settle within the first five minutes, eg excessive discomfort, or a suspicion that the lens is inverted, then the lens may be removed and a new lens reapplied.

[REDACTED]

[REDACTED]

[REDACTED]

[REDACTED]

[REDACTED]

[REDACTED]

[REDACTED]

[REDACTED]

- 10. The subject will be asked to score the following subjective scores, with reference to appropriate vertical analogue scales [REDACTED]

- Comfort

[REDACTED]

[REDACTED]

- Overall score

- 11. The subject will then be discharged and asked to return approximately 2 hours later.

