**3.2.3 Visit 1b (follow-up)**

The following procedures will be performed:

- 1. The subject will be asked to score the following reactions:

- Comfort before removal
- Dryness

[REDACTED]

[REDACTED]

[REDACTED]

- Overall score

[REDACTED]

[REDACTED]

5. The lenses will be removed and discarded.

[REDACTED]

7. A complete biomicroscopic examination will be conducted as outlined in Visit 1.
8. The subject will then be discharged and asked to return for Visit 2. Subjects are reminded to attend wearing spectacles, and not to wear habitual contact lenses on the day of the visit.

### 3.2.4 Visit 2

The following procedures will be performed (any ocular measurement procedures outlined below will be carried out on each eye):

1. Medical and ocular history since the last visit will be recorded.

[REDACTED]

3. Slit lamp Biomicroscopy will be carried out for the signs outlined in Table 5 and in accordance with the current Eurolens Research Standard Operating Procedure 'Examination of the anterior segment using slit lamp Biomicroscopy'. Grades will be scored to the nearest 0.1 unit in the best judgement of the investigator using Efron Grading Scales. Corneal staining will be graded for five regions as described in [REDACTED]

Classification	Primary signs	Secondary signs
Signs	
[REDACTED]
 
Corneal staining Location of staining
 
[REDACTED]
	
[REDACTED]

Scale	Efron Grading Scales (scored to nearest 0.1) Corneal staining (see [REDACTED])	Efron Grading Scales (scored to nearest 0.1 except mucin balls, where the number is recorded)

Table 5: Biomicroscopic signs. Staining assessed with sodium fluorescein.

The presence of any ocular adverse events will be recorded, and reported as appropriate [REDACTED]

4. Subjects who have Type 2 or greater corneal staining and or corneal staining covering greater than 20% in any corneal region may be brought back for up to one repeat visit of this type, which may include some or all of the scheduled assessments.
5. Study lenses will be fitted according to the randomization table and allowed to settle for five minutes. Both investigator and subject are masked from the lenses and care system used, so the lenses will be provided in lens cases which do not detail lens or care system information. If a lens fails to settle within the first five minutes, e.g. excessive discomfort, or a suspicion that the lens is inverted, then the lens may be removed and a new lens reapplied.

[REDACTED]

[REDACTED]

[REDACTED]

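### Do the unmatched visit labels and loose replacement wording for corneal staining before lenses at Visit 2 put the result at risk?

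*Combined protocol and SAP*

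**What the plan says.** Section 2.1.4 has two staining exclusions. Criterion 10 reads "They have Type 2 or greater corneal staining prior to lens application at Visit 1 or 2". Criterion 11 reads "They have corneal staining covering greater than 20% in any corneal region at Visit 1a or 2a". Both lines end in a redaction.

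Section 3.1 states "Subjects will be required to attend four visits across two different days" and lists them as 1, 1b, 2 and 2b, the same labels as in Table 1.

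Four places bear on a subject who breaches a limit:

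- Section 2.2: "Subjects who fail to meet all the inclusion and exclusion criteria at this time will usually be discontinued and replaced". It then allows up to one repeat visit for a subject who may be eligible later. It names no visit.
- Section 3.2.2 (Visit 1, step 5) has nearly the same sentence, beginning "Subjects who fail to meet all the criteria at this time will usually", and there it clearly belongs to Visit 1.
- Section 3.2.4 (Visit 2, step 4) permits a single repeat and words it as follows: "Subjects who have Type 2 or greater corneal staining and or corneal staining covering greater than 20% in any corneal region may be brought back".
- Section 2.1.1: "Subjects who have signed the consent form, but who have not completed the dispensing visit will usually be replaced". Section 2.6.3 provides for two dispensing visits.

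On data, section 2.1.1 says "All subject data will be included in the final analyses unless there are strong grounds for exclusion", and section 3.4 admits partial datasets where appropriate. On numbers, sections 1.5.1 and 2.1 recruit 28 subjects to complete 22.

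**The concern.** Read one at a time, the passages seem to give different outcomes for one subject: over a staining limit before lenses at Visit 2, having completed day 1. Section 2.1.4 makes that subject ineligible. Section 2.2, if it is general, usually discontinues and replaces. Section 3.2.4 offers an optional repeat visit and does not say what happens if the staining is still there. Section 2.1.1 provides for replacement or is silent, depending on which dispensing visit it means. Criterion 11 adds labels that appear in no schedule.

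This deserves a check because corneal staining is also the principal outcome (section 1.5.1), and a loss at this point leaves half a crossover. If staff followed different passages, the number of completers could vary. If day-1 data were also discarded, subjects would be removed on a variable related to the outcome, which could in principle distort the comparison of solutions.

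**Working it through.** **1. Which visit criterion 11 means.** Section 3.2.4 places both limits (type, and extent above 20% in a region) after the slit-lamp examination and before lens fitting at Visit 2. The label 2a is therefore most naturally the pre-lens part of Visit 2, and 1a that of Visit 1. This is an inference: no visible text defines the labels, although the redacted line endings may.

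**2. Whether the handling passages conflict.** They can be read as layers. Section 2.1.4 sets eligibility. Section 2.2 gives the usual action plus a discretionary single repeat visit. Section 3.2.4 restates that discretion at Visit 2 in similar terms. Sections 2.2 and 3.2.4 agree on the repeat option, and their wording is permissive. What remains open is whether section 2.2 reaches Visit 2, and hence whether a subject lost there is replaced.

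**3. The plan's power figure.** Inputs from section 1.5.1: difference 5, SD of intra-subject differences 8, two-sided alpha 0.05, paired analysis, 22 completers. Power is the probability that a noncentral t variable with n − 1 degrees of freedom and noncentrality (5/8)√n lies beyond the two-sided critical value.

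- n = 22: noncentrality 0.625 × √22 = 2.93, power 0.798. The stated 0.80 is reproduced.

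**4. Power under either reading.** The allowance is 28 − 22 = 6 subjects, or 6/28 = 21.4%.

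| Complete pairs | 28 | 27 | 26 | 25 | 24 | 23 | 22 |
|---|---|---|---|---|---|---|---|
| Power | 0.890 | 0.878 | 0.865 | 0.850 | 0.834 | 0.817 | 0.798 |

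Without replacement, losses move the study rightwards along this row. With replacement, it stays further left. Neither reading falls below the plan's own figure unless total unreplaced losses, from all causes, exceed 6 (0.778 at 21, 0.755 at 20). The documents give no expected rate of Visit 2 staining failures.

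**5. Day-1 data.** The default in section 2.1.1 is inclusion. Because the lenses are worn as an unmatched pair (section 2.6.3), a subject lost at Visit 2 still contributes a within-subject lens comparison for the first solution. Only the between-solution comparison needs both days.

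**6. If day-1 data were dropped, contrary to that default.** As an illustration only, assume a correlation of 0.3 between first-day staining and pre-lens staining at Visit 2, a between-day correlation of 0.5, and the top 21.4% removed. A true solution difference of 5 then becomes about 4.97 among complete pairs, or about 4.95 if replacements restore equal order groups. The shift is 0.03 to 0.05 units on a 0-100 scale. Neither correlation comes from the documents, so the verdict does not rest on this.

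**The case for a change.** The strongest case for acting is that the gap survives every reading. If section 2.2 is confined to Visit 1, its tension with section 3.2.4 disappears, but Visit 2 failures then have no replacement rule. If it is general, its default (discontinue and replace) differs from the optional repeat in section 3.2.4. Either way, nothing at Visit 2 says what follows a failed repeat visit. The correction would also be cheap, since only wording is involved.

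That stands as an editorial point. The passages must be reconciled on this case; which handling is right is a clinical matter and is not addressed here.

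The argument that replacement would push enrolment past 28 carries little weight. Section 2.1.1 counts enrolment from consent and also provides for replacing enrolled subjects, so a replaced Visit 1 failure has the same effect. Reporting losses by first solution would be a reasonable extra, but section 2.2 already has all discontinuations recorded and section 3.4 already has the number of subjects in each analysis reported.

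The line in section 3.2.5 that asks subjects at Visit 2b to return for Visit 2 is a separate sentence carried over from Visit 1b. The next paragraph treats the visit as final, with exit statement and payment, so it should mislead nobody.

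**Conclusion.** No change to the design, sample size or analysis follows. The slips are genuine: labels in criterion 11 that are absent from the schedule, a time reference in section 2.2 with no visit attached, a singular dispensing visit in section 2.1.1, and a carried-over sentence in section 3.2.5. They are clerical or matters of missing detail, to be reconciled in ordinary editing. The claim that the plan prescribes contradictory outcomes goes too far, because the passages can be read together and the uncertainty narrows to whether a Visit 2 failure is replaced.

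On size, the stated power of 0.80 at 22 completers holds, with a range of 0.798 to 0.890 over the six allowed losses. This rests on the plan's own difference and SD, on total unreplaced losses of no more than 6, and on analysts following the stated default of keeping available day-1 data. Under those conditions no bias or loss of planned power is shown.

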#### 2.2 Subject discontinuation

In general, subjects should be discontinued at any time, if it is in their best interests, as judged by the investigator. Reasons for this may include clinical signs of grade 3 or more, lack of motivation, discomfort, repeated refusal to follow instructions or the use of non-study products such as solutions or lenses. Subjects will be discontinued if a serious adverse event occurs or if they miss two or more planned consecutive visits. Subjects who fail to meet all the inclusion and exclusion criteria at this time will usually be discontinued and replaced. If in the opinion of the investigator, the subject may be eligible at a later date, the subject may be brought back for up to one repeat visit of this type. Subjects may choose to leave the study at their own request. All discontinuations will be carefully recorded.

### **2.3 Safety parameters, adverse events and concurrent illnesses**

The key safety parameters are the serious and significant adverse events listed in [REDACTED] (adverse events are classified as 'serious', 'significant' or 'non-significant'). Clinical assessment is made at the study visit(s) for these parameters. The presence of any ocular adverse event will be noted on the eCRF and reported to the Sponsor using CVI report forms and those ocular adverse events described as 'serious' or 'significant' will be detailed in the final report. Similarly, any concurrent illness will be noted on the eCRF and comment added if is likely to impact on the relevance and quality of the captured data.

#### **2.3.1 Investigator obligations**

At all times the investigator will act in the best interest of the subject. Referral or treatment of an adverse event or other clinical finding should be initiated in the best clinical judgement of the investigator, irrespective of the participation in the clinical study.

#### **2.3.2 Reporting obligations**

Non-significant ocular adverse events should be reported to the Industrial Contact Person within 5 working days. In the case of a 'serious' or 'significant' adverse ocular event, the Principal Investigator and the Industrial Contact Person will be notified within 24 hours. Manchester UREC and any regulatory authorities will be informed as required.

### **2.4 Study termination**

If it becomes necessary to terminate the study earlier than planned, the Industrial Contact Person will notify the Principal Investigator who will end the study with the cooperation of other staff members. Manchester UREC will be informed.

### **2.5 Protocol deviations**

Any deviations from this protocol will be recorded on the eCRF, and reported to the Industrial Contact Person as appropriate. Manchester UREC will be informed as necessary. Device deficiencies will be recorded on the eCRF and reported to the Industrial Contact Person as appropriate.

#### **2.5.1 Protocol amendments**

Any amendments will be agreed between the Industrial Contact Person and the Principal Investigator with the cooperation of other staff members. Amendments will be recorded, identified and distributed. Approval from Manchester UREC will be obtained as necessary.

## 2.6 Study resources

### 2.6.1 Lenses

Details of the study lenses are provided in Table 2. All lens types are CE marked.

Name	Avaira Vitality	Biofinity
Manufacturer	CooperVision Inc.	CooperVision Inc.
Material	Fanfilcon A	Comfilcon A
EWC (%)	55	48
BOZR (mm)	8.4	8.6
Diameter (mm)	14.2	14.0
Spherical powers (D)	-0.25D	-0.25D

Table 2: Study lenses.

#### 2.6.1.1 Use of lenses

Lenses will be worn for the short duration (approximately 2 hours) required in this study.

### 2.6.2 Care regimen

Details of the care regimens used in this study are provided in Table 3. All solutions are CE marked.

Name	Lite (US formulation)	Hy-Care (EU formulation)
Manufacturer	CooperVision Inc.	CooperVision Inc.
Active ingredients	Polyhexanide	Polyhexanide

Table 3: Care regimens.

#### 2.6.2.1 Use of care regimen

Lenses will be removed from blister packaging and stored directly in solution for between 12 to 72 hours before being worn for approximately 2 hours by the subject. All lenses will be stored in generic contact lens cases supplied by the Sponsor. Contact lens cases will be pre-conditioned on arrival at the site prior to use on the study.

### 2.6.3 Randomization of lenses and care regimens

This is a double-masked (participant, investigator), contralateral, crossover study design. Lenses are worn as an unmatched pair. In order for subjects to use each possible combination of lens/solution, two dispensing visits will be required. The order of lens/solution use is detailed in the randomization schedule (██████████). The randomization will be such that across the two study days, each eye will wear both of the study lenses. That is, if for the first solution the randomization determines that the right lens will wear the Avira Vitality lens and the left eye will wear the Biofinity lens, the laterality of the lenses will be swapped for the second solution.

#### 2.6.4 Inventory control

All study lenses and study solutions will be supplied by CooperVision Inc. Worn lenses will usually be discarded, and any opened bottles of solution disposed of. Where possible, lenses associated with device deficiencies will be retained (stored in sterile saline), and returned to the Sponsor unless otherwise directed.

All unused materials will be returned to the Sponsor at the end of the study unless the site is otherwise directed by the Sponsor:

[REDACTED]

#### 2.6.5 Clinical equipment

Clinical equipment is regularly maintained and calibrated as required. Standard operating procedures and international standards are used where appropriate.

#### 2.7 Study control

This study is controlled by cross-comparison. Bias will be minimized by masking and randomizing the order of assessment. Masking may be 'broken' if deemed necessary, by the Principal Investigator or Industrial Contact Person.

#### 2.8 Documentation

Documents related to this work that require archiving will be kept by Eurolens Research for a period of 10 years after completion of the final report. The Sponsor's permission will be sought before the documents are destroyed.

#### 2.9 Data collection and analysis

Data collected in this work will be recorded on a custom-developed database (eCRF) and an established data trail. Data handling will include export of the study information from the clinical database into spreadsheet format for manipulation, followed by export into a statistical package for analysis. Most clinical data will be entered directly onto the electronic case report form and is considered to be source data.

#### 2.10 Study completion

The clinical phase of the study will be considered as complete when all subjects have received\* and/or signed the exit statement. (\*In the event that a subject is lost to follow-up.)

**2.11 Confidentiality**

All matters related to this work will remain confidential within Eurolens Research, the funding company and any regulatory authority (e.g. Manchester UREC). Eurolens Research will take all reasonable steps to ensure that specific lens-related information is not passed on to study participants unless this is required for clinical management of an adverse event. Personal subject information will not be made available. To cater for this, subjects will only be referred by their unique identity number in the study report. The data activities of Eurolens Research are registered with the data protection officer at The University of Manchester.

